7.1 Study Intervention/Device Description

Enrolled subjects will receive either PR or LVDS platelets based on the group to which they have been randomized. Both products are generally available in the blood bank, considered equally safe and efficacious, and used as standard of care.

7.2 Availability

As both products are already supplied to the blood banks at both Weill Cornell and Columbia, no special ordering will be required. Given shortages in the blood supply that are increasingly more common, the study coordinators in transfusion medicine at each site will work with the clinical research coordinators to ensure the product availability for the upcoming scheduled surgeries.

7.3 Acquisition and Accountability

Not applicable

7.4 Formulation, Appearance, Packaging, and Labeling

As the study is unblinded, the PR and LVDS platelets will maintain their normal appearance, packaging and labeling as required and approved by the FDA.

7.5 Product Storage and Stability

The blood products will be stored as per normal protocol in the blood banks at each site.

7.6 Preparation

The blood products will be prepared as per standard protocols maintained in the blood banks at each site.

7.7 Dosing and Administration

Platelets will be prescribed and administered at the discretion of the clinical teams. Each platelet transfusion will be dosed as 10mL/kg as per standard of care.

7.7.1 Dosing Delays/Dose Modifications

Not applicable

7.8 General Concomitant Medication and Supportive Care Guidelines

All hemostatic medications and blood products (such as anti-fibrinolytics, plasma transfusions and cryoprecipitate) will be prescribed at the discretion of the clinical team. All concomitant medications will be recorded in the REDCap data collection tool.

7.9 Duration of Therapy and Criteria for Removal from Study

In the absence of treatment delays due to adverse event(s), treatment may continue for the first 24 hour post-operatively or until one of the following criteria applies:

- Unacceptable adverse event(s),
- Subject decides to withdraw from the study, or
- General or specific changes in the subject's condition render the subject unacceptable for further treatment in the judgment of the investigator.

A subject's follow-up in the study will end after one of the following applies:

- Subject's voluntary withdrawal
- Subject death
- Completion of all scheduled study follow-up appointments

7.10 Duration of Follow Up

Subjects will be followed until discharge from the hospital after removal from study or until death, whichever occurs first. Subjects removed from study for unacceptable adverse events will be followed until resolution or stabilization of the adverse event.

7.11 Measures to Minimize Bias: Randomization and Blinding

Stratified and permuted blocked randomization will be performed. A series of randomized blocks with a defined block size will be generated for each participating site with a 1:1 allocation ratio. This will allow for an equal number of patients in the PR platelets group and LVDS platelets group at each participating site (even in the event that full target accrual is not achieved). Randomization will be stratified by site (Komansky Children's Hospital/Weill Cornell vs. Morgan Stanley Children's Hospital/Columbia) and STAT score (STAT 1/2 vs. STAT 3/4/5). A biostatistician from the Weill Cornell CTSC Biostatistics, Epidemiology and Research Design (BERD) Core will create the randomization list and will not be involved with the study. The randomization list for each site will also reside in the Research Pharmacy at each site. Only the BERD statistician and the Research Pharmacies will have a copy of the blocked randomization list (for their respective sites). As this is an open-label study, all study personnel will be aware of the treatment assignments. The blocked randomization schemes for each participating site will be uploaded to a central REDCap database (housed at Weill Cornell Medicine) and each site's Research Pharmacy will be able to randomize a patient at their site by using the REDCap randomization module.

7.12 Study Intervention/Follow-up Compliance

No applicable

8. Study Intervention Discontinuation and Participant Discontinuation/Withdrawal

Participants may withdraw voluntarily from the study or the PI may discontinue a participant from the study. Patients will be discontinued if they require extracorporeal membrane oxygenation (ECMO) post-operatively (as the volume of platelet transfusions that a child requires on ECMO will likely not feasibly be supported by only one type of platelets). A dedicated Case Report Form (CRF) page will capture the date and the specific underlying reason for discontinuation of study intervention or participant discontinuation/withdrawal.

8.1 Discontinuation of Study Intervention

Those children who unexpectedly require support from ECMO following surgery will be discontinued from the study intervention (as their need for platelet transfusions and risk of bleeding will be different due to the extracorporeal circulation of their blood). The decision to remain on ECMO is made in the operating room and the study team will be informed by the clinical team. Also, if a patient requires re-cannulation onto ECMO within the first 24 hours post-op (while in the PICU), they will be discontinued in the study intervention. There are no reasons for temporary discontinuation.

Discontinuation from platelet transfusion strategy does not mean discontinuation from the study, and remaining study procedures should be completed as indicated by the study protocol. If a clinically significant finding is identified (including, but not limited to changes from baseline) after enrollment, the investigator or qualified designee will determine if any change in participant management is needed. Any new clinically relevant finding will be reported as an adverse event (AE).

The data to be collected at the time of study intervention discontinuation will include the following: Outcome Evaluation, Medical Record Review and Data Collection, Adverse Events Assessment.

8.2 Participant Discontinuation/Withdrawal from the Study

Participants are free to withdraw from participation in the study at any time upon request. An investigator may discontinue or withdraw a participant from the study for the following reasons:

- If any clinical adverse event (AE), laboratory abnormality, or other medical condition or situation occurs such that continued participation in the study would not be in the best interest of the participant
- If the participant meets an exclusion criterion (either newly developed or not previously recognized) that precludes further study participation

The reason for participant discontinuation or withdrawal from the study will be recorded on the Case Report Form (CRF). Subjects who sign the informed consent form and are randomized but do not receive the study intervention may be replaced. Subjects who sign the informed consent form, and are randomized and receive the study intervention, and subsequently withdraw, or are withdrawn or discontinued from the study, will be replaced.

8.3 Lost to Follow Up

Not applicable (as the entire study occurs while the subject is admitted to the hospital)

9. Correlative/Special Studies

Not applicable

9.1 Laboratory Correlative Studies

Not applicable

9.2 Special Studies

Not applicable

10. Measurement of Effect

10.1 Response Criteria

The effect of the platelet transfusions received intra-operatively and in the first 24 hours post-op will be measured by (1) chest tube output in the first 24 hours post-op and (2) total transfusions required in the first 48 hours post-op

10.2 Duration of Response

Though transfused platelets typically stay in circulation for 5-7 days, we will be measuring the hemostatic efficacy for the first 24 hours post-operatively.

10.3 Progression-Free Survival

Not applicable

10.4 Other Response Parameters

Though not directly related, clinical outcomes, such as mortality, length of hospital stay, length of PICU stay, length of mechanical ventilation and length of vasoactive therapy will be collected.

11. Data Reporting / Regulatory Considerations

11.1 Data Collection

The data collection plan for this study is to utilize REDCap to capture all treatment, toxicity, efficacy, and adverse event data for all enrolled subjects.

11.1.1 REDCap

REDCap (Research Electronic Data Capture) is a free data management software system that is fully supported by the Weill-Cornell Medical Center CTSC. It is a tool for the creation of customized, secure data management systems that include Web-based data-entry forms, reporting tools, and a full array of security features including user and group based privileges, authentication using institution LDAP system, with a full audit trail of data manipulation and export procedures. REDCap is maintained on CTSC-owned servers that are backed up nightly and support encrypted (SSL-based) connections. Nationally, the software is developed, enhanced and supported through a multi-institutional consortium led by the Vanderbilt University CTSA.

11.2 Regulatory Considerations

11.2.1 Institutional Review Board/Ethics Committee Approval

As required by local regulations, the Investigator will ensure all legal aspects are covered, and approval of the appropriate regulatory bodies obtained, before study initiation.

Before initiation of the study at each study center, the protocol, the ICF, other written material given to the patients, and any other relevant study documentation will be submitted to the appropriate Ethics Committee. Written approval of the study and all relevant study information must be obtained before the study center can be initiated or the IP is released to the Investigator. Any necessary extensions or renewals of IRB approval must be obtained for changes to the study, such as amendments to the protocol, the ICF,

or other study documentation. The written approval of the IRB together with the approved ICF must be filed in the study files.

The Investigator will report promptly to the IRB any new information that may adversely affect the safety of the patients or the conduct of the study. The Investigator will submit written summaries of the study status to the IRB as required. On completion of the study, the IRB will be notified that the study has ended.

All agreed protocol amendments will be clearly recorded on a protocol amendment form and will be signed and dated by the original protocol approving signatories. All protocol amendments will be submitted to the relevant institutional IRB for approval before implementation, as required by local regulations. The only exception will be when the amendment is necessary to eliminate an immediate hazard to the trial participants. In this case, the necessary action will be taken first, with the relevant protocol amendment following shortly thereafter.

Once protocol amendments or consent form modifications are implemented at the lead site, Weill Cornell Medicine, updated documents will be provided to participating sites, as applicable. Weill Cornell Medicine must approve all consent form changes prior to local IRB submission.

Relevant study documentation will be submitted to the regulatory authorities of the participating countries, according to local/national requirements, for review and approval before the beginning of the study. On completion of the study, the regulatory authorities will be notified that the study has ended.

11.2.2 Ethical Conduct of the Study

The Investigators and all parties involved should conduct this study in adherence to the ethical principles based on the Declaration of Helsinki, GCP, ICH guidelines and the applicable national and local laws and regulatory requirements.

This study will be conducted under a protocol reviewed and approved by the applicable ethics committees and investigations will be undertaken by scientifically and medically qualified persons, where the benefits of the study are in proportion to the risks.

11.2.3 Informed Consent

The investigator or qualified designee must obtain documented consent according to ICH-GCP and local regulations, as applicable, from each potential subject or each subject's legally authorized representative prior to participating in the research study. Subjects who agree to participate will sign the approved informed consent form and will be provided a copy of the signed document.

The initial ICF, any subsequent revised written ICF and any written information provided to the subject must be approved by IRB prior to use. The ICF will adhere to IRB requirements, applicable laws and regulations.

Participants will be consented remotely using an electronic version of the informed consent form that follows federal, state, and local regulations, as applicable. We will

implement the following procedures for electronic informed consent.

The informed consent document(s) will be sent to the subject or their Legal Authorized Representative (LAR), if applicable, via secure email sent by REDCap prior to the scheduled consent discussion. The subject or LAR will be asked to review the consent document prior and during the consent discussion with a study staff member via an approved teleconferencing service (i.e., Zoom). The study staff member will confirm the subject or LAR has read and has the capacity to appreciate all aspects of the information presented in the consent process for the research study. The subject or LAR will be encouraged to ask questions. If agreeing to participate, the subject or LAR will sign the consent form using electronic informed consent (eConsent) via REDCap. A computer, tablet or touch screen phone will be used to capture digital signatures. If applicable, the person conducting consent will also sign the electronic informed consent (eConsent) document in a contemporaneous manner. Subjects will be provided with a digital copy of the completed form via email. The informed consent discussion and process will be documented by the study team in the subject's medical record or study record.

If a subject does not have access to a touch screen phone, computer or tablet, cannot work with remote electronic informed consent, or the remote electronic informed consent cannot be obtained for any other reasons, the consent may be conducted and documented at an in-person visit prior to study activities via paper consent form or through REDCap on an ITS tagged device.

11.2.4 Compliance with Trial Registration and Results Posting Requirements

Under the terms of the Food and Drug Administration Modernization Act (FDAMA) and the Food and Drug Administration Amendments Act (FDAAA), the Sponsor-Investigator of the trial is solely responsible for determining whether the trial and its results are subject to the requirements for submission to <http://www.clinicaltrials.gov>. Information posted will allow subjects to identify potentially appropriate trials for their disease conditions and pursue participation by calling a central contact number for further information on appropriate trial locations and trial site contact information.

11.2.5 Record Retention

Essential documents are those documents that individually and collectively permit evaluation of the study and quality of the data produced. After completion of the study, all documents and data relating to the study will be kept in an orderly manner by the Investigator in a secure study file. Essential documents should be retained for 2 years after the final marketing approval in an ICH region or for at least 2 years since the discontinuation of clinical development of the IP. In addition, all subjects medical records and other source documentation will be kept for the maximum time permitted by the hospital, institution, or medical practice.

12. Statistical Considerations

Due to feasibility and limited resources, a sample size of 126 patients will be included in this study. A sample size of 63 patients (126 total) in each group achieves 90% power

to detect a minimum difference of 0.2 mL/kg/hr in chest tube output 24 hours after the cardiopulmonary bypass surgery between the group receiving pathogen-reduced (PR) platelet transfusions and the group receiving standard (large volume delayed sampling – LVDS) platelet transfusions using a two-sample t-test assuming equal variance with a two-sided significance level of 0.05.

Based on preliminary data, only around 50% of children who undergo cardiopulmonary bypass surgery require platelet transfusions. Therefore, 252 patients will be enrolled and randomized to the study to take that into consideration.

Descriptive statistics (means, medians, standard deviations, interquartile ranges, proportions, frequency, and percent) will be calculated for baseline characteristics to assess and describe the study participants (by treatment group). Baseline comparability will be assessed using two-sample t-test (or Wilcoxon-rank sum test) for continuous baseline characteristics and the chi-square test (or Fisher's exact test) for categorical baseline characteristics.

Based on the understanding that 50% of the randomized participants will receive treatment, the following populations will be formed for the purpose of data analysis:

- An intent-to-treat cohort, defined as all participants who were recruited into the study, will be used for the primary and secondary analyses in the arm in which they were randomized, regardless of whether treatment was given.
- Per-protocol cohort, defined as all participants that continue with the platelet transfusion (PR platelets or LVDS platelets)

All analyses will be performed in R Version 4.0.5 (R Foundation for Statistical Computing, Vienna, Austria). Note: The statistical considerations section was written in conjunction with [name] MS, in the Division of Biostatistics, Department of Population Health Sciences.

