12.2 Sample Size/Accrual Rate

252 subjects will be randomized 1:1 to pathogen-reduced (PR) platelet transfusions or standard (large volume delayed sampling – LVDS) platelet transfusions. Randomization will be done in REDCap using blocks of varying sizes and stratified by site and STAT score. We anticipate only 50% of children will require a transfusion, leaving evaluable 63 patients per arm. With 63 patients per arm (126 total), and assuming a standard deviation of 0.4, we will have 90% power to detect a minimum mean difference of 0.2 between the two treatment arms with a significance level of 0.050 using a two-sided two-sample equal-variance t-test.

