12.4 Analysis of Endpoints

12.4.1 Analysis of Primary Endpoints

The primary endpoint in this study is the chest tube output for the first 24 hours following cardiopulmonary bypass surgery. A two-sample t-test assuming equal variance or a non-parametric Wilcoxon rank-sum test will be used, as appropriate. All tests will be two-sided with an alpha level of 5%. Confidence intervals for the difference in means will also be calculated to assess precision.

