12.5 Interim Analysis

The DSMB will conduct regular reviews regarding the efficacy or futility of the treatment. If patients receiving PR platelets have > 20% bleeding as compared to LVDS platelets at the time of the interim analysis, the trial will be stopped. **Interim analyses will be conducted by the study team three times during the course of the study with the enrollment and transfusion of every 42 patients.**

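### The stated 90% power is about 80% on the plan's own inputs, covers only the transfused children, and no power is given for the intention-to-treat primary analysis

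*Combined protocol and SAP*

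**What the plan says.** The opening of section 12 (Statistical Considerations) states: "A sample size of 63 patients (126 total) in each group achieves 90% power", for a difference of 0.2 mL/kg/hr with a two-sided 5% equal-variance t-test. Section 12.2 repeats the claim and supplies the missing input: "assuming a standard deviation of 0.4, we will have 90% power to detect a minimum mean difference of 0.2 between the two treatment arms".

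Section 12.2 also says who the 63 per arm are: "We anticipate only 50% of children will require a transfusion, leaving evaluable 63 patients per arm". They are the expected transfused half of 252 children randomised 1:1. The interim schedule in section 12.5 counts the same children, with a look "with the enrollment and transfusion of every 42 patients", three times (3 × 42 = 126).

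The primary analysis is given to a different group. Section 12 says that the intention-to-treat cohort, meaning everyone recruited, "will be used for the primary and secondary analyses in the arm in which they were randomized, regardless of whether treatment was given". That is about 126 per arm.

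Section 4.6 (Strategies for Recruitment and Retention) gives another basis for the same 126 transfused children: a difference of 1 mL/kg/hr with 80% power.

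**The concern.** There are three difficulties with the trial's headline design figure.

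- Section 12.2 gives every input needed to check the 90%, and the figure does not follow from them.
- The figure is computed on transfused children, while the primary test will be run on all randomised children. About half of these are expected to receive no platelets, so the assigned product has no direct route to affect their bleeding. The difference being tested should then be smaller than the 0.2 in the power statement.
- Section 4.6 names a target difference five times as large, at a different power, for the same number of children.

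An ethics board, monitoring board or later reader would take from section 12 that a true 0.2 mL/kg/hr difference has a one-in-ten chance of being missed in the primary analysis. The plan does not support that. It matters more because section 3.1 hypothesises that the two products are equivalent: a non-significant result looks more reassuring when the test is believed to have 90% power.

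**Working it through.** **Inputs.** n = 63 per arm, SD 0.4, difference 0.2, two-sided 0.05, equal-variance two-sample t-test (section 12.2; unit mL/kg/hr from section 12). 252 randomised, 50% expected to be transfused (sections 12 and 12.2).

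**1. The plan's own figure.**
- Standardised difference: 0.2 / 0.4 = 0.5.
- Noncentrality: 0.5 × √(63/2) = 2.806.
- Normal approximation: Φ(2.806 − 1.960) = Φ(0.846) = 0.801.
- Noncentral t with 124 degrees of freedom: 0.795.

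The stated 90% is not reproduced. The type II error is about 20.5% (1 − 0.795), about double the 10% implied.

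**2. Could another reading give 90%?**

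| Variant | Power |
|---|---|
| One-sided 0.05 | 87.4% |
| Two-sided 0.10 | 87.4% |
| Two-sided 0.025 | 70.4% |
| Wilcoxon under normality | 77.6% |
| 126 per arm, undiluted 0.2 | 97.7% |

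None comes within 2 points of 90%.

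**3. Working backwards.** Sample size per arm is 2 × (z for alpha + z for power)² × (SD/difference)².
- 80% power: 2 × (1.960 + 0.842)² × 4 = 62.8, so 63. This is exactly the plan's number.
- 90% power: 2 × (1.960 + 1.282)² × 4 = 84.1, so 85; the t-test needs 86.
- Holding n = 63, 90% needs a standardised difference of 0.582. That means an SD of 0.2 / 0.582 = 0.344, or a difference of 0.582 × 0.4 = 0.233.

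**4. Section 4.6.** With n = 63 and 80% power, the detectable standardised difference is 0.503. A difference of 1 mL/kg/hr then implies an SD of 1 / 0.503 = 1.99, about five times 0.4. Section 4.6 states neither alpha nor test, so this assumes those of section 12.2.

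**5. Intention-to-treat illustration (assumptions, not plan figures).** Assume 50% transfused in each arm, no effect of assigned product in untransfused children, and SD 0.4 for all randomised children.
- Diluted difference: 0.5 × 0.2 + 0.5 × 0 = 0.1.
- Noncentrality: (0.1 / 0.4) × √(126/2) = 1.984.
- Power: Φ(1.984 − 1.960) = 0.510; noncentral t 0.507.

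The result depends heavily on the assumed SD. With the same diluted difference, an SD of 0.3 gives 75% and an SD of 0.5 gives 35%.

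**The case against.** The strongest defence is that this is a pilot sized by feasibility, that section 3.1 openly expects about half the children to go untransfused, and that section 12.4.1 plans an interval as well as a test: "Confidence intervals for the difference in means will also be calculated to assess precision". All of that is true, and it is why no increase in sample size is called for. It does not rescue an explicit 90% that its own inputs contradict, and it does not supply a power for the primary set.

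It can also be said that the power may be right and an input misreported: an SD near 0.34 or a difference near 0.233 would give 90%. That stands as a possibility. The exact match of 63 with the 80% formula, and the 80% in section 4.6, point towards a slip in the power figure but do not prove it. The sponsor has to check.

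A reader might infer more than the documents support:

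- **That intention-to-treat power is known to be about 51%, or to lie in some definite range.** The documents give no mean or SD for untransfused children, and they do not say whether 0.4 applies to all randomised children. The figure is an illustration.
- **That the primary set is unnamed, or that untransfused or replaced children might drop out of it.** Section 12.4.1 names no set, but the opening of section 12 does, and it keeps everyone recruited in the assigned arm.
- **That the transfused comparison is unusable as planned.** Section 12 provides a cohort: "Per-protocol cohort, defined as all participants that continue with the platelet transfusion (PR platelets or LVDS platelets". Sections 6.1.2 and 6.1.2.2 fix the window, from the operating room through 24 hours after surgery. The definition is loosely worded, but that is missing detail and not part of this error. Nor do the documents require a different supportive set to be substituted.

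**Conclusion.** The point holds. On the documents' own inputs, power for the transfused comparison is about 80% (79.5%), not 90%; this part rests on no outside assumption. Section 4.6 conflicts with sections 12 and 12.2 on both the target difference and the power. The implied SD of about 2.0 depends on carrying over the alpha and test from section 12.2.

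It is also firm that the stated power belongs to about 63 transfused children per arm, while the primary analysis covers about 126 randomised children per arm with no power stated. How far power falls in that analysis cannot be settled from the documents. Under the labelled assumptions it is about 51%, and the true figure may be higher or lower.

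The power statement must be corrected before it is relied on. The finding does not show that the trial is too small for a pilot or that the primary set should change.

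**What to change.** 1. Check the original calculation. Unless an input was misreported, change 90% to about 80% in the opening of section 12 and in section 12.2, and label it as the power for the transfused children (63 per arm, difference 0.2 mL/kg/hr, SD 0.4, two-sided 5%). If an input was misreported, correct that input in both places.
2. Reconcile section 4.6 with sections 12 and 12.2, so that one target difference, one SD and one power support the 63 per group.
3. State separately the power, or the detectable difference, of the intention-to-treat primary analysis with about 126 per arm. Give the assumed share transfused, the dilution and the SD for all randomised children. The retrospective study of 140 children in section 3.2 may provide that SD, if its data allow.

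The cost is protocol and SAP wording only, with no added patients and no change of primary set. The downside is that the stated power becomes less favourable.

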1.1 Schema

1.2 Study Objectives and End Points

1.2.1 Primary Objectives

To determine the amount of post-operative bleeding in children receiving PR versus LVDS platelet transfusions during and following cardiopulmonary bypass surgery.

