3.1 Overall Design

This is a multisite, open-label, randomized trial of PR versus LVDS platelet transfusions in children undergoing cardiopulmonary bypass surgery. The study will be conducted at Komansky Children's Hospital at Weill Cornell and Morgan Stanley Children's Hospital at Columbia. Given that both products are FDA approved and already used in this patient population, it is a Phase IV study. Based on our preliminary retrospective data, we hypothesize that both products will have equivalent hemostasis, as measured by chest tube output in the first 24 hours, as well as total blood component requirements. Given the complexity of surgery is associated with bleeding risk, the two groups will be stratified on a validated score of surgical complexity (STS scoring). All subjects will be enrolled in the study for the length of their hospitalization.

The need for platelet transfusion will not be dictated by the study intervention, but rather the clinical team (both in the operating room and post-operatively, in the pediatric intensive care unit). Given that we do not want to delay the release of blood products from the blood bank, but rather have them available as standard of care in the operating

room, we cannot randomize the subjects at the time of the decision to transfuse platelets. Therefore, we will randomize subjects before the day of surgery. We recognize that there will be a significant number of randomized subjects (approximately 50%) who do not receive a platelet transfusion. Data will be collected on this group and analyzed both separately, and in an intention to treat model.

All platelet transfusions will be given as 10mL/kg as is considered standard of care.

Given the need to cross-check any transfusion of the blood component for patient safety, no area of the labeling will be disturbed and therefore the clinicians caring for the patients will be unblinded. Those responsible for data entry and data analysis will be blinded to the assigned groups of the subjects.

To minimize bias, we will perform subgroup analyses of neonates versus all other children given that the neonatal coagulation system is still under development and different than the coagulation system of the older child.

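### The primary analysis is ITT although about half of each arm receives neither product, and the transfused children have no specified final analysis, so an ITT result alone cannot support the hypothesised equivalent hemostasis

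*Combined protocol and SAP*

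**What the plan says.** All references are to the combined protocol and SAP.

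- **Section 12, opening text.** Two populations are introduced with the words "the following populations will be formed for the purpose of data analysis". The first, the intent-to-treat cohort of all recruited participants, "will be used for the primary and secondary analyses in the arm in which they were randomized, regardless of whether treatment was given". The second is a "Per-protocol cohort, defined as all participants that continue with the platelet transfusion (PR platelets or LVDS platelets"). No endpoint, test or interpretive role is attached to the second.
- **Sections 12.4.1 and 12.4.2.** These name the tests (t-test or Wilcoxon for chest tube output and transfusion totals, chi-square or Fisher for infections) but no population. The primary test is two-sided at 5%, with a confidence interval for the difference in means.
- **Section 3.1.** The expectation is stated as "we hypothesize that both products will have equivalent hemostasis, as measured by chest tube output in the first 24 hours". About 50% of randomized children are expected to go untransfused, and of them the plan says "Data will be collected on this group and analyzed both separately, and in an intention to treat model".
- **Section 1.2.1.** The objective is post-operative bleeding "in children receiving PR versus LVDS platelet transfusions".
- **Section 12.2.** The sample size rests on recipients: "We anticipate only 50% of children will require a transfusion, leaving evaluable 63 patients per arm". The assumed SD is 0.4 and the difference to detect is 0.2.
- **Sections 12.5 and 15.** Interim looks are counted in transfused patients, and the stopping rule compares children receiving the two products.

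**The concern.** The question, the sample size and the interim monitoring all concern children who receive platelets. Only the final analysis moves to a population of which about half receives neither product. A product cannot change bleeding in a child who never receives it, so those children pull the arm difference toward zero.

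For a claim that the products differ, this is conservative. For a claim that they are similar, which is what Section 3.1 expects, it works the other way: dilution makes a real difference among recipients look smaller. If a non-significant ITT test or a tight ITT interval were read as confirming equivalence, a product that is less hemostatic in the children who received it could be described as similar. The plan specifies no final analysis in recipients that would check that reading.

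**Working it through.** **Inputs from the documents.** 252 randomized 1:1, so 126 per arm; 50% transfused, so 63 per arm; SD 0.4; difference 0.2 (mL/kg/hr in the Section 12 opening text); two-sided alpha 0.05 (Sections 12 and 12.2).

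**Assumptions.** The assigned product has no effect in untransfused children. The transfused share is equal in both arms. The limit of ±0.2 is borrowed from the detectable difference, because the plan states no equivalence margin. Normal approximation throughout.

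**1. The plan's own power figure.** For 63 per arm, SE = 0.4 × √(2/63) = 0.0713. Power = Φ(0.2/0.0713 − 1.96) = 80% (79.5% with the noncentral t), not the stated 90%. That is a separate discrepancy, and nothing below depends on it.

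**2. Dilution.** ITT difference = transfused share × difference among recipients = 0.5 × 0.2 = 0.1. For 126 per arm, SE = 0.4 × √(2/126) = 0.0504. Power of the planned ITT test = Φ(0.1/0.0504 − 1.96) = 51%.

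**3. Chance that the 95% CI lies inside ±M.** With true difference d in the cohort analysed, P = Φ((M − 1.96·SE − d)/SE) − Φ((−M + 1.96·SE − d)/SE). Put M = 0.2 and a true difference of 0.2 among recipients.

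- Transfused cohort (d = 0.2, SE 0.0713, half-width 0.140): Φ(−1.96) − Φ(−3.65) = 2.5%.
- ITT (d = 0.1, SE 0.0504, half-width 0.099): Φ(0.02) − Φ(−3.99) = 51%.

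**4. A larger SD in the mixed population.** Section 12.2 states SD 0.4 for the evaluable transfused children. If transfused children bleed g mL/kg/hr more on average than untransfused ones (assumption), the ITT SD is √(0.4² + 0.5 × 0.5 × g²).

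| g | ITT SD | ITT SE | P(ITT 95% CI inside ±0.2) |
|---|---|---|---|
| 0 | 0.400 | 0.0504 | 51% |
| 0.4 | √0.20 = 0.447 | 0.0563 | 43% |
| 0.8 | √0.32 = 0.566 | 0.0713 | 28% |

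**5. Transfused share.** At SD 0.4, a 40% share gives d = 0.08 and P = 66%; a 60% share gives d = 0.12 and P = 36%.

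**6. Other limits.** Set the true difference among recipients equal to M (ITT difference M/2), with SD 0.4 and a 50% share.

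| M | ITT | Transfused cohort |
|---|---|---|
| 0.1 | Φ(−0.97) − Φ(−1.02) = 1% | 0% (half-width 0.140 exceeds M) |
| 0.2 | 51% | 2.5% |
| 0.3 | Φ(1.02) − Φ(−6.97) = 85% | 2.5% |

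The size depends on the limit. With a limit as tight as 0.1 neither population could show similarity at this sample size. At 0.2 and above, the two populations give very different answers.

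**The case against.** Four objections deserve weight.

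**The transfused children are not ignored.** A reader might infer that they play no part in the trial's conclusion. The documents do not support that. Both populations are formed for analysis, the trial is sized on recipients, interim looks occur at every 42 transfused, and the stopping rule compares recipients. The third look falls at 3 × 42 = 126, the full transfused target. What stands is narrower: no final primary or secondary analysis is specified for them. The stopping rule acts in one direction and is not a similarity analysis. The group that Section 3.1 analyses separately is the untransfused one.

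**The plan contains no equivalence test.** A reader might infer that the design secures an equivalence finding. It does not. Section 3.1 states an expectation, the planned test is a two-sided difference test for which dilution is conservative, and Section 2.4.1 says it is unknown whether either product is less efficacious. The risk arises only if a null or narrow ITT result is then read as equivalence. The plan states that hypothesis and has no rule against that reading.

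**The percentages are not competing error rates.** In the scenario the ITT difference truly is 0.1, inside the limit, so 51% is not a type I error for the ITT quantity. It is how often ITT would look reassuring when recipients differ by the whole limit. It also depends on a borrowed margin and on the SD in the mixed population.

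**The transfused cohort is not protected by randomization.** Transfusion is discretionary and decided after randomization by unblinded clinicians (Sections 3.1 and 7.11), so knowledge of the arm could affect who is transfused. This is a real weakness. It is the reason to require both analyses and not to replace ITT.

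**Conclusion.** The point holds in a limited form. Section 12 gives the primary and secondary analyses to a population in which about half receive neither product, and specifies no final analysis for the population that the objective and sample size describe. If untransfused children have no product difference, the ITT difference is about half the difference among recipients. ITT alone therefore cannot carry a conclusion of equivalent hemostasis.

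With an assumed limit of ±0.2 and a true difference of 0.2 among recipients, the ITT interval falls inside the limit in 51% of trials, or 43% or 28% under the larger mixture SDs, against about 2.5% in the transfused cohort. The direction is firm, while the size moves with the margin, the transfused share and the SD. The documents do not show that an equivalence claim would be made on ITT, only that the plan leaves it open.

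**What to change.** In Section 12:

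1. Prespecify an analysis of chest tube output in all transfused children by randomized arm, and define that cohort clearly. The present wording, which refers to participants who continue with the transfusion, does not.
2. State an equivalence margin in advance, with its justification. Conclude similar or equivalent hemostasis only if the 95% CI in that cohort and the 95% CI in ITT both lie within it.
3. Keep ITT for any claim of a difference.
4. Report by arm the proportion transfused and the use of the non-assigned product. Section 2.4.1 allows the available product to be given when the assigned one is not available, and analysis by randomized arm leaves that source of dilution in place.

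**Cost.** A short addition to Section 12 and no new patients. The transfusion data are already planned, and the margin needs clinical agreement before results are seen. An equivalence claim becomes harder to reach: with no true difference, SD 0.4 and a limit of ±0.2, the 95% CI falls inside in 2Φ((0.2 − 0.140)/0.0713) − 1 = 60% of trials in the transfused cohort, against 2Φ((0.2 − 0.099)/0.0504) − 1 = 96% in ITT. The transfused cohort is also open to selection after randomization by unblinded clinicians, so it must be read alongside ITT and never alone.
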